#### 8.1 Sample size consideration

The target is to recruit at least 50 patients for each of basal cell carcinoma group, malignant melanoma group and benign dry skin conditions group. We anticipate at least 80% of patients who meet eligibility criteria to accept to enrol, that is, recruitment rate is at least 80%. For eligibility rate, we consider the worst case scenario (50% eligibility rate) and low eligibility rate of 20%. We consider three cases of willingness rates (20%, 50% and 80%). Table 1 shows the sample sizes and margins of error (ME), where ME =  $1.96 \times \sqrt{\frac{rate \times (1-rate)}{sample \, size}}$ . The largest number needed to be approached is 1575 patients for each group. As highlighted in the table, we expect a scenario requiring to approach 630 to be closer to the reality. The largest margin of error corresponds to the recruitment rate at 9.9% so that the 95% CI is 70%-90%. We consider this to precise enough for recruitment rate.

For comparing means, power is lowest for independent t-tests. With 50 patients in each group, assuming a moderate effect size (standardised difference of 0.5), the power is 80% at 10% significance level.

Table 1: Sample sizes and margins of errors

Willingness rate	20%	20%	50%*	50%	80%	80%
Eligibility rate	20%	50%	20%*	50%	20%	50%
Recruitment rate	80%	80%	80%*	80%	80%	80%
Willingness: n †	1575	630	630	252	394	158
ME	2.0%	3.1%	3.9%	6.2%	3.9%	6.2%
Eligibility: n ‡	315	126	315	126	315	126
ME	4.4%	8.7%	4.4%	8.7%	4.4%	8.7%
Recruitment: n§	63	63	63	63	63	63
ME	9.9%	9.9%	9.9%	9.9%	9.9%	9.9%

†Corresponds to number approached to be screened; ‡Corresponds to number screened for eligibility; §Corresponds to number eligible; \*Expect reality closer to this scenario.

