## Study arm 2 - patients only:

- Aged 18 years and over
- Confirmed or suspected skin cancer (incompletely excised BCC with histologically proven radial margin involvement, biopsy proven BCC or pigmented lesions suspicious of malignant melanoma).
- Diagnosed with an incompletely excised basal cell carcinoma skin cancer (either radial margin involvement on primary excision or following diagnostic punch biopsy).

- Clinically suspicious pigmented skin lesion (suspected melanoma) with a plan for surgical biopsy
- Capacity to give informed consent

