## 8. STATISTICS AND DATA ANALYSIS

The summary of the study process from approaching a patient about the study to collecting their data at the study visit consists of the following steps

- 1. Step 1: During a clinic visit, a patient will be approached to check whether they are willing to be screened and enrol in the study. We will record the number of patients that are approached and how many are willing to enrol in the study.
- 2. Step 2: For each patient willing to enrol, a study visit will be scheduled. A record of whether a patient comes for a scheduled study visit will be kept.
- 3. Step 3: Eligibility will be assessed during the study visit.
- 4. Step 4: If a patient is eligible, they will be asked whether they are still willing to be part of the study, that is, whether they consent to be enrolled/recruited in the study.

The process will continue until at least 150 patients are recruited in the study; 50 for benign dry skin conditions group and 100 in the skin cancer group (we will aim for 50 basal cell carcinoma patients and 50 malignant melanoma patients).

Data collected in step 1 will be used to estimate the rate of willingness to enrol in the study. It will be computed as the proportion of approached patients who indicate they are willing to enrol in the study. A conservative estimate for the rate of willingness will combine information in steps 1 and 2, where patients who do not come for the study visit are considered not willing to enrol in the study. Eligibility rate, computed using data in step 3, will be proportion of eligible patients among those assessed for eligibility. Proportion of eligible patients that are recruited will give the recruitment rate. These rates will be computed for the three study groups (benign dry skin conditions, basal cell carcinoma and malignant melanoma) separately.

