For all consenting eligible patients, during the study visit, outcomes will be taken for the affected (area of interest) and unaffected (control) parts of the skin. For each group, a paired t-test will be used to compare the means of outcomes (e.g. skin hydration) for affected and unaffected parts. The corresponding mean difference between affected and unaffected parts and 95% confidence interval (CI) will also be reported. For affected parts, using one way analysis of variance (ANOVA), we will test whether the means for the three groups are equal. Pairwise comparisons using independent t-tests will also be performed, with mean difference and 95% CI reported. We will also compare unaffected parts means for the three groups similarly.

Since this is a feasibility study, we will test all hypotheses at 10% significance level. Also, we will not adjust for multiplicity associated with testing multiple hypotheses. However, for it to be worthwhile conducting a future large study to test utility of THz, clear signals (large differences), estimated using mean differences and 95% CIs, will need to be observed in this feasibility study.

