#### 8.2 Planned recruitment rate

Approximately 6000 new 2WW referrals for suspected skin cancer are reviewed within the Department of Dermatology at UHCW per year. With over 100 new referrals per week, and a known conversion rate of 2-3% for biopsy proven melanoma, around 2 to 3 new cases of melanoma will be diagnosed per week. Within the study recruitment period, the planned number of patients recruited to both study arms should be achieved. Although a temporary reduction was noted in the referral patterns at the onset of COVID-19, these numbers returned to pre-COVID-19 levels within a matter of months. If a "second wave" or further incidence of COVID-19 causes similar disruption, then possible delays in recruitment may be incurred.

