# 8.3 Participant population

The patients will be recruited from scheduled Dermatology out-patient clinics including routine general Dermatology clinics and staff members working at UHCW NHS Trust (study arm 1: dry skin conditions) OR two week wait (2WW) urgent Dermatology clinics for suspected skin cancer, and joint clinics run between Dermatology and Plastic Surgery (study arm 2: known or suspected skin cancer). Patients will be selected based on clinical diagnosis. Patients will not be randomised.

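### The 50 malignant melanoma patients are enrolled on suspicion before histology, so the stated 80% power applies to confirmed melanoma only if all 50 lesions are confirmed

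*Protocol*

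**What the plan says.** - **Target.** Section 8.1 asks for "at least 50 patients for each of basal cell carcinoma group, malignant melanoma group and benign dry skin conditions group". The sample size row of the Study Summary and the recruitment paragraph of section 8 likewise count 50 malignant melanoma patients.
- **When recruitment stops.** Section 8: "The process will continue until at least 150 patients are recruited in the study". The count is of patients recruited, not of diagnoses confirmed.
- **Entry.** Section 6.1, study arm 2: "Clinically suspicious pigmented skin lesion (suspected melanoma) with a plan for surgical biopsy". Section 1.3 and the study arms row of the Summary also describe this group as suspected. Section 8.3 adds: "Patients will be selected based on clinical diagnosis".
- **Histology.** Under section 7.3 it is taken from the medical records, typically 2 to 4 weeks after biopsy and so after the scan. Section 9.1 links it to the scan data.
- **Outcome.** Section 3.4 sets the secondary outcome on skin in which melanoma is present, with the end point reached once scans have been compared with histology.
- **Analysis.** Section 8 plans paired t-tests within each group, then an ANOVA and pairwise t-tests across three groups, one of them named malignant melanoma. It does not say whether membership follows suspicion or histology.
- **Power.** Section 8.1: "With 50 patients in each group, assuming a moderate effect size (standardised difference of 0.5), the power is 80% at 10% significance level".
- **Recruitment argument.** Section 8.2 relies on "a known conversion rate of 2-3% for biopsy proven melanoma, around 2 to 3 new cases of melanoma will be diagnosed per week".

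**The concern.** The same label covers two populations. The eligibility criteria admit suspicious pigmented lesions; the target, the group tests, the power statement and the recruitment argument speak of melanoma. Unless every suspected lesion is confirmed, the analysed group is a mixture, and its mean combines melanomas with lesions of other kinds.

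This matters because section 8 makes a larger study depend on clear, large differences in these group means. A melanoma signal could be weakened by the other lesions in the group, or a signal from those lesions could be reported as melanoma. A reader would also take 80% to be the power for melanoma, which the plan does not secure. The willingness, eligibility and recruitment rates would carry a melanoma label although they describe patients with suspected lesions.

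**Working it through.** **Inputs from the protocol.** 50 per group, standardised difference d = 0.5 and a 10% level (8 and 8.1: "we will test all hypotheses at 10% significance level"). Sidedness is not stated. The expected scenario in Table 1 of section 8.1 has 630 approached, 50% willing, 20% eligible and 80% recruited. The 2-3% conversion rate is given against all new two-week-wait referrals (8.2).

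**Input not in the protocol.** The share of suspicious pigmented lesions planned for biopsy that are confirmed as melanoma. It is an assumption here and is shown as a range.

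**Step 1: reproduce the stated power.** For an independent t-test with m and n patients, the noncentrality is d × √(mn/(m+n)) on m+n−2 degrees of freedom. With 50 and 50 it is 0.5 × √25 = 2.5. At a two-sided 10% level, power is 79.9% (normal approximation 80.4%). A one-sided 10% test would give 88.6%, so two-sided is the reading that matches. The 80% is right for two groups of 50.

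**Step 2: the same test with only confirmed melanomas**, against 50 basal cell carcinoma patients, d = 0.5, two-sided 10%:

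| Confirmed of 50 | Share | Noncentrality | Power |
|---|---|---|---|
| 5 | 10% | 0.5 × √(250/55) = 1.07 | 28% |
| 8 | 16% | 0.5 × √(400/58) = 1.31 | 37% |
| 15 | 30% | 0.5 × √(750/65) = 1.70 | 52% |
| 25 | 50% | 0.5 × √(1250/75) = 2.04 | 65% |
| 35 | 70% | 0.5 × √(1750/85) = 2.27 | 73% |
| 50 | 100% | 2.50 | 80% |

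Any confirmation rate below 100% leaves power below the stated figure.

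**Step 3: what the protocol's own rates imply, under stated assumptions.** If the 630 approached were unselected two-week-wait referrals, they would include 630 × 2% to 630 × 3% = 12.6 to 18.9 melanomas. If every melanoma is eligible, willingness and recruitment leave 12.6 × 0.5 × 0.8 = 5.0 to 18.9 × 0.5 × 0.8 = 7.6, that is 5 to 8 among about 50 enrolled. Both conditions are assumptions. Sections 7.1 and 7.1.1 point to some selection before approach, from clinical review, referral letters or photographs, and this would raise the share. The first two rows of the table are therefore one scenario, not a forecast.

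**Step 4: the population in section 8.2.** At 100 referrals a week, 2-3% gives 2 to 3 biopsy-proven melanomas a week, or 104 to 156 a year. That counts confirmed disease. The protocol enrols suspicious pigmented lesions planned for biopsy and gives no figure for how many of those the clinic sees.

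**The case against.** The power figure is not an arithmetic error, and it applies to the groups as recruited. The Summary's arm description, section 1.3 and section 6.1 openly say suspected. Sections 1.3, 1.4, 3.4 and 9.1 commit to comparing or linking scans with histology, and the detail of that comparison may sit in a statistical analysis plan that is not shown. The primary objective is feasibility, the melanoma objective is exploratory, and progression rests on clear signals rather than on power. All of this stands and lowers the severity. It does not remove the conflict, because the protocol itself fixes the target, the three groups, the tests and the power, and these do not agree with its entry criterion and its outcome.

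Three stronger readings are tempting, and the documents do not support them:

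- *Only one or two of the 50 will be melanoma.* This applies the 2-3% directly to the group. That rate is a yield among all two-week-wait referrals, not among pigmented lesions suspicious enough for planned biopsy.
- *The centre cannot supply 50 melanomas in the recruitment year.* This would pass confirmed melanomas through the 20% eligibility rate as well. That rate is the share of all those screened who qualify; a patient with melanoma would normally meet the criterion. With willingness and recruitment alone, 104 to 156 a year × 0.5 × 0.8 gives about 42 to 62, provided every such patient is approached. The pool is not shown to be too small.
- *The group would mostly be benign lesions.* That depends entirely on a confirmation rate the protocol does not give. The size of any dilution of the group mean also depends on how non-melanoma pigmented lesions scan, which is unknown.

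**Conclusion.** The concern holds as an internal conflict: a group enrolled on suspicion is counted, tested and powered as 50 melanoma patients, with no allowance for non-confirmation and no stated use of histology in section 8. The 80% is valid for 50 versus 50 as recruited. For confirmed melanoma it is an upper limit, reached only if all 50 are confirmed. Between 5 and 35 confirmed, power against 50 basal cell carcinoma patients runs from 28% to 73%, given d = 0.5, a two-sided 10% level and a comparator group that reaches 50. Where in that range, or above it, the trial will fall cannot be told from the protocol. This should be fixed, but it does not undermine the primary feasibility objective.

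**What to change.** 1. In the Study Summary, section 8 and section 8.1, call the group *suspected melanoma*. State an assumed confirmation rate with a range and the expected number confirmed. Limit the 80% statement to comparisons of groups as recruited with 50 each, and give the power for the expected number of confirmed melanomas beside it.
2. In section 8, define the melanoma comparisons by histology: confirmed melanoma, with histologically benign pigmented lesions shown separately, each as a mean difference with a 95% CI. Keep the suspicion-based group for the feasibility rates and as a descriptive comparison.
3. In section 8.2, base the recruitment argument on the number of suspicious pigmented lesions planned for biopsy, the population actually enrolled.

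The cost is protocol wording. Histology is already collected for arm 2 and linked to the scans, so no new data are needed. The downside is a less favourable stated power for melanoma.

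### The 80% power figure is presented as the lowest for any comparison of means, but the planned three-group ANOVA can have as little as 71%; separately, 10% tests are paired with 95% intervals

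*Protocol*

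**What the plan says.** Protocol section 8 plans three kinds of comparison of means:

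- a paired t-test of affected against unaffected skin within each group;
- a three-group comparison of affected skin: "using one way analysis of variance (ANOVA), we will test whether the means for the three groups are equal";
- pairwise independent t-tests between the groups.

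The between-group comparisons are repeated for unaffected skin. The level is common to all: "Since this is a feasibility study, we will test all hypotheses at 10% significance level". Mean differences are reported with 95% confidence intervals. A future large study is made conditional on seeing "clear signals (large differences), estimated using mean differences and 95% CIs, will need to be observed in this feasibility study".

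Section 8.1 supports the comparisons of means with two sentences. The first ranks the methods: "For comparing means, power is lowest for independent t-tests". The second gives the figure: "With 50 patients in each group, assuming a moderate effect size (standardised difference of 0.5), the power is 80% at 10% significance level". No power is given for the ANOVA, and no pattern of the three group means is assumed.

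**The concern.** A statement that power is lowest for one method tells the reader that every other planned comparison of means does at least as well. Here that reads as 80% or better throughout for a difference of 0.5 SD. An F test on three groups spreads its sensitivity over two degrees of freedom. It can therefore be less powerful than a t-test aimed at the two groups that differ most. If so, the stated floor does not exist.

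The second issue is the pairing of levels. A 95% interval corresponds to a 5% test. When the tests run at 10%, the same comparison can be declared significant while its interval includes zero. The only power figure given describes the 10% test, whereas section 8 looks to the 95% interval when it speaks of a signal.

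**Working it through.** **Inputs.** From section 8.1: n = 50 per group and d = 0.5 (SD = 1 on the standardised scale). From section 8: three groups, tests at 10%, intervals at 95%. The protocol does not state whether the level is one- or two-sided. Two-sided reproduces its figure, and one-sided gives about 89%, so two-sided is used.

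**1. The protocol's own figure.** For an independent t-test, df = 2 × 50 − 2 = 98 and the noncentrality is d × √(n/2) = 0.5 × √25 = 2.5. The two-sided 10% critical value is 1.661. Power from the noncentral t distribution is 79.9% (80.4% by the normal approximation). The stated 80% reproduces.

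**2. The ANOVA at the same level.** The degrees of freedom are 2 and 150 − 3 = 147, and the 10% critical value of F is 2.339. The noncentrality is λ = n × Σ(μᵢ − μ̄)². The largest pairwise difference is held at 0.5 SD and the third mean is moved:

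| Group means (SD units) | λ | Power at 10% |
|---|---|---|
| 0, 0.25, 0.5 | 50 × (0.25² + 0² + 0.25²) = 6.25 | 71.2% |
| 0, 0.1, 0.5 | 50 × (0.2² + 0.1² + 0.3²) = 7.00 | 75.7% |
| 0, 0, 0.5 | 50 × (2 × 0.1667² + 0.3333²) = 8.33 | 82.3% |

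λ is smallest when the third mean is midway, so 71.2% is the minimum for this largest difference, and 82.3% is the maximum. ANOVA power equals the t-test's 79.9% when the third mean lies about 0.034 SD inside either extreme. Anywhere further in, the ANOVA is the weaker test. That covers (0.5 − 2 × 0.034)/0.5, or about 86%, of the positions between the two extremes. Reaching 80% with the third mean midway would take 63 per group.

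**3. Tests at 10% against intervals at 95%.** With 50 against 50, the standard error of the difference in SD units is √(2/50) = 0.2.

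- The smallest observed difference significant at 10% is 1.661 × 0.2 = 0.33 SD.
- The smallest observed difference whose 95% interval excludes zero is 1.984 × 0.2 = 0.40 SD.

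Between these two values the test is significant and the interval includes zero. At a true difference of 0.5 SD, the 95% interval excludes zero with 69.7% probability (noncentral t, two-sided 5%). The chance of landing in the zone of disagreement is 79.9% − 69.7% = 10.2%.

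**4. The paired t-tests.** Their power depends on the within-patient correlation, which the protocol does not give. Taking 0.5 as the difference divided by the SD of a single area, the 10% power is 79.4% at correlation 0, 83.0% at 0.1 and 96.7% at 0.5 (assumed values). Among the t-tests, the independent one is therefore the weakest unless the correlation is close to zero or negative.

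**The case against.** The strongest reply is that no stated number is wrong. The 80% is correct and is tied explicitly to the independent t-test. The pairwise t-tests are planned alongside the ANOVA and do not depend on its being significant, so their power is unaffected. That stands, and it limits the error to the ranking sentence.

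A second reply is that 71% is a worst case. That also stands. A reader might infer that the planned ANOVA simply has 71% power, but the protocol assumes no pattern of means, and with two equal means the ANOVA has 82%, above the t-test. If neighbouring groups each differed by 0.5 SD (means 0, 0.5 and 1), it would have 99.8%. The range does not rescue the sentence, because a claim about the lowest power has to hold in the least favourable case.

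On the intervals, a reader might infer that the decision on a future trial has only 70% power. The protocol does not support that. It sets no rule that a 95% interval must exclude zero; it asks for large differences, judged with intervals. At 0.8 SD, an assumed meaning of large, the 95% interval excludes zero with 97.7% probability. A demanding second look after liberal tests is also a reasonable design, and the protocol openly declares both the 10% level and the absence of multiplicity adjustment. Neither choice is a fault. What remains is that test and interval for the same comparison can point different ways, and the protocol does not say how such a result is to be read.

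**Conclusion.** Wrong as written. The statement that power is lowest for independent t-tests is not a property of this design. For a largest pairwise difference of 0.5 SD at the 10% level, ANOVA power is 71% to 82%, and it is below the t-test's 80% unless the third mean lies within about 0.034 SD of an extreme. This assumes equal groups of 50, normal outcomes with a common SD and two-sided testing.

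The mismatch between 10% tests and 95% intervals is real but smaller. It affects observed differences of about 0.33 to 0.40 SD in the 50 against 50 comparisons.

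The consequence is modest. The primary objective and outcomes (sections 3.1 and 3.3) concern feasibility, and these comparisons are secondary. Neither point calls for a change in the sample size.

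**What to change.** In section 8.1, replace the ranking sentence with a statement such as: power is 80% for an independent t-test with 50 per group at a standardised difference of 0.5 and a two-sided 10% level; for the three-group ANOVA it is 71% to 82% when the largest difference is 0.5 SD, depending on the third mean. Alternatively, limit the statement about lowest power to the t-tests, noting that this presumes a positive within-patient correlation for the paired comparisons.

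In section 8, do one of two things:

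- report 90% intervals alongside the 10% tests; or
- keep the 95% intervals and add that such an interval excludes zero with about 70% power at 0.5 SD.

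The cost is a few sentences, and one stated power figure becomes less favourable. Recruitment, procedures and group sizes are untouched.

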#### 8.2 Planned recruitment rate

Approximately 6000 new 2WW referrals for suspected skin cancer are reviewed within the Department of Dermatology at UHCW per year. With over 100 new referrals per week, and a known conversion rate of 2-3% for biopsy proven melanoma, around 2 to 3 new cases of melanoma will be diagnosed per week. Within the study recruitment period, the planned number of patients recruited to both study arms should be achieved. Although a temporary reduction was noted in the referral patterns at the onset of COVID-19, these numbers returned to pre-COVID-19 levels within a matter of months. If a "second wave" or further incidence of COVID-19 causes similar disruption, then possible delays in recruitment may be incurred.

## 8.2.1 Summary of baseline data and flow of patients

Patient age, sex, location of anatomical area of interest to be scanned and provisional clinical diagnosis will be collected as baseline data. This will be analysed to investigate the recruitment process to improve recruitment during the SINATRA study period and in future similar studies.

